### Secondary Endpoints

- To compare overall survival between the treatment and placebo arms
- To compare duration on study treatment between the treatment and placebo arms
- To compare the best overall RECIST response rate between the treatment and placebo arms
- To compare and correlate the 2-week CEHPI perfusion index and 8 week RECIST response rates in the ITT population
- To compare the median overall survival of patients receiving Axitinib who develop new diastolic hypertension ( $>90\text{mmHg}$ ) with those that do not (in either/or the blinded placebo group or treatment group combined)
- To identify if CEHPI will function as a correlative biomarker of Axitinib pharmacokinetics (PK) and help minimise toxicity and identify responders
- To compare toxicity (CTC) information for the treatment and placebo arms.
  - Type, incidence, severity, timing, seriousness of adverse events by Chemotherapy toxicity criteria (CTC) v4.03 grading.
- Axitinib PK analysis correlation with patients developing or not developing diastolic hypertension

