The conventional PFS and OS for this cohort of chemo-refractory patients is 6-8 weeks and 4-6 months respectively. This is the first study with Axitinib in this setting. Our aim with 50 patients is to generate data for a sample size calculation for a randomised phase III. In the only comparative Phase 2 study (A6181003) with a similar compound, is of Sunitinib in chemorefractory metastatic colorectal cancer, 84 patients were enrolled and 82 were actually treated with Sunitinib. 10% discontinued due to adverse events. The ITT analyses for PFS was less than 2 months but OS still showed an encouraging overall survival of 10.2 months. Of greater interest, 1 patient with prior Bevacizumab therapy had a partial response; 24 patients (29%) had a best response of stable disease, 13 patients had SD  $\geq 22$  weeks. (This demonstrates the reason for doing our analysis as a sub-population has benefited significantly from Axitinib's parent compound and with CEPHI – we hope to predict this group). In our study, we would thus expect around 15-18 of the treated patients to have prolonged progression-free survival of this order of magnitude, and the placebo treated patients will act as a contemporaneous control. If the 2 week CEPHI index is highly predictive of survival in this group, then selection on this basis for a phase III trial will enrich the potentially benefitting population even further.

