## 9.2 Statistical analysis plan

The primary analysis will be on PFS by Kaplan-Meier of patients who manage to complete at least 2 weeks of Axitinib therapy (versus Placebo).

For the secondary analyses:-

A stratified log-rank test (1-sided,  $p=0.025$ ) will be used to compare PFS between CEHPI responders and non-responders. The median event time and 2-sided 95% CI for the median will be provided. The hazard ratio and its 95% CI will be also estimated.

The optimum CEHPI cut-point for determining response will be confirmed using the percentage change in CEHPI against RECIST response using a receiver operator characteristic curve. Test statistics including sensitivity, specificity, positive predictive value, negative predictive value, odds of disease progression and area under the curve will be calculated for 2 week CEHPI reduction in predicting disease progression.

A similar analysis will be performed with diastolic blood pressure.

Overall survival is defined as the time from date of randomisation to date of death due to any cause. For patients not expiring, their survival times will be censored at the last date they are known to be alive. Patients lacking data beyond the day of randomisation will have their survival times censored at the date of randomisation with duration of 1 day. Overall survival will be summarised using Kaplan-Meier methods and displayed graphically where appropriate. A stratified log-rank test (1-sided,  $p=0.025$ ) will be used to compare OS between CEHPI responders and non-responders. The median event time and 2-sided 95% CI for the median will be provided. The hazard ratio and its 95% CI will be also estimated.

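### Section 9.2 gives log-rank tests and hazard ratios only for CEHPI groups; the listed overall survival comparison of Axitinib with placebo has no specified test or hazard ratio, and by-arm PFS has Kaplan-Meier only

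*Combined protocol and SAP*

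**What the plan says.** The Trial Summary, section 2.1 and section 2.2 all list the same randomised comparison for OS: "To compare overall survival between the treatment and placebo arms".

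Section 9.2 measures OS from randomisation to death from any cause and sets censoring rules. Its descriptive statement is: "Overall survival will be summarised using Kaplan-Meier methods and displayed graphically where appropriate". No grouping is given. The only OS test is a stratified one-sided log-rank test at 0.025 that "will be used to compare OS between CEHPI responders and non-responders". The median with its interval and the statement "The hazard ratio and its 95% CI will be also estimated" come directly after it.

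PFS is handled in parallel. The log-rank test "will be used to compare PFS between CEHPI responders and non-responders", again followed by the median and hazard ratio. The one analysis by arm is this: "The primary analysis will be on PFS by Kaplan-Meier of patients who manage to complete at least 2 weeks of Axitinib therapy (versus Placebo"). It carries no test, alpha or hazard ratio.

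Section 9.1 gives the purpose of the data: "Our aim with 50 patients is to generate data for a sample size calculation for a randomised phase III".

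**The concern.** The trial randomises 50 patients 2:1, and section 9.1 calls the placebo patients a contemporaneous control. Yet every test and hazard ratio that 9.2 names compares patients by the change in CEHPI at 2 weeks. That split is observed after treatment starts, so randomisation does not balance it. Someone who dies or leaves before the scan cannot be classified.

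This goes further than leaving a method unnamed. The plan picks a test, an alpha level and an estimator, and attaches them to groups other than those in its own OS endpoint. A statistician following 9.2 literally would report an OS hazard ratio that does not answer the listed question, and no hazard ratio for Axitinib against placebo on either OS or PFS. Sizing a phase III in unselected patients calls for the randomised effect and its uncertainty.

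**Working it through.** **What is specified for each comparison**

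| Comparison | Listed in 2.1 or 2.2 | Kaplan-Meier in 9.2 | Log-rank test in 9.2 | Hazard ratio in 9.2 |
|---|---|---|---|---|
| OS, Axitinib v placebo | Yes, secondary | Summary with no grouping stated | None | None |
| PFS, Axitinib v placebo | Yes, co-primary | Yes, patients completing at least 2 weeks | None | None |
| OS, CEHPI groups | Not as a separate endpoint; described in 9.1 | Grouping not stated | Yes | Yes |
| PFS, CEHPI groups | Yes, co-primary | Medians given | Yes | Yes |

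Section 9.2 also promises a similar analysis by diastolic blood pressure. Those groups are not randomised either. No other section supplies a by-arm test or hazard ratio.

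**What a by-arm analysis could deliver**

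The documents state no power, event count or target hazard ratio, so there is no figure to reproduce. What follows is illustration.

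Inputs from the documents: 50 patients, 2:1; one-sided 0.025 (stated only for the CEHPI tests); control PFS 6–8 weeks and control OS 4–6 months, taken as medians (9.1).

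Assumptions: exponential times; 40 to 50 events; a 6-week gain by arm. Section 9.1 gives 6 weeks as the observed PFS improvement that would trigger a phase III application. For survival it gives 6 weeks only for the CEHPI groups, so using it for OS by arm is an assumption.

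Precision. With 2:1 allocation the information is events × (2/3)(1/3) = events × 2/9, and the 95% interval factor is exp(1.96/√(events × 2/9)).

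- 50 events: exp(1.96/3.333) = 1.80
- 45 events: exp(1.96/3.162) = 1.86
- 40 events: exp(1.96/2.981) = 1.93

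Power (Schoenfeld) = Φ(|ln HR| × √(events × 2/9) − 1.96), with HR = control median/(control median + gain). Six weeks is 1.38 months.

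- OS, 45 deaths, control 4 months: HR = 4/5.38 = 0.744; power 15%
- OS, 45 deaths, control 5 months: HR = 5/6.38 = 0.784; power 12%
- OS, 45 deaths, control 6 months: HR = 6/7.38 = 0.813; power 10%
- PFS, 50 events, control 6 weeks: HR = 6/12 = 0.50; power 64%
- PFS, 50 events, control 8 weeks: HR = 8/14 = 0.571; power 46%

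Over 40 to 50 deaths the OS power runs from 9% to 17%. Reaching 80% for OS would take about 403 deaths (control 4 months) to 825 (control 6 months). As an example of precision, an observed OS hazard ratio of 0.744 with 45 deaths would have an interval of about 0.744/1.86 = 0.40 to 0.744 × 1.86 = 1.38. The by-arm OS analysis is therefore an estimate with an interval, not a powered test.

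**The case against.** Four arguments can be made for the plan, and each limits what can be claimed.

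First, a reader might infer that OS by arm would have no result at all. The text does not support that. The Kaplan-Meier summary names no groups and could be shown by arm. The OS censoring rules also cover patients with no data after randomisation, who can have no 2-week scan. What is missing is a specified test and hazard ratio.

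Second, a reader might infer that the CEHPI comparisons ignore treatment arm. The plan specifies a stratified test and does not name the strata, so arm could be one of them. The text shows only that arm is not the factor compared.

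Third, the CEHPI survival comparison is deliberate. Section 9.1 calls better patient selection the major interest of its secondary and exploratory work and envisages an enriched phase III, for which CEHPI-group estimates matter. By-arm medians are also usable sizing inputs, and the 6-week PFS trigger can be read from Kaplan-Meier curves. This stands, and it is why the CEHPI analyses should stay. It does not remove the by-arm endpoint from section 2.2.

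Fourth, section 9.1 concedes that 50 patients are too few for adequate power. That argues against leaning on a p-value. It does not argue against reporting the by-arm estimate and interval, since the plan already reports hazard ratios for CEHPI groups within the same 50 patients.

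**Conclusion.** The point holds as a gap between the listed endpoint and the specified analysis. Section 9.2 contains two log-rank tests and two hazard ratios, all between CEHPI groups, and none between randomised arms for OS or PFS. The CEHPI hazard ratios cannot replace the randomised effect, because the groups are non-randomised and leave out patients without a 2-week scan.

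That conclusion rests on the text alone. The figures only show what a by-arm estimate would be worth: an interval factor of about 1.8 to 1.9 each way for 50 down to 40 events, and OS power of about 10% to 15% with 45 deaths, exponential times and an assumed 6-week gain by arm. It would be tempting to treat that OS gain as the plan's own by-arm target, but section 9.1 states it for the CEHPI groups only. The documents also give no basis for saying how far the CEHPI hazard ratios would lie from the by-arm ones.

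**What to change.** In section 9.2:

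- For OS, add Kaplan-Meier curves by arm, a hazard ratio with 95% interval and a log-rank test, Axitinib v placebo, in all randomised patients. Label this as estimation, because the trial is not powered for it.
- For PFS, add a by-arm hazard ratio with 95% interval in all randomised patients. State openly that this population differs from the 2-week completers now named for the primary analysis, which can stay as a supporting analysis.
- Name these by-arm estimates, together with the by-arm medians, as the input for sizing an unselected phase III.
- Keep the CEHPI comparisons as the planned biomarker analyses, and name the strata of the log-rank tests, including whether arm is one.

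The cost is a few sentences of plan text and standard output. Section 6.6 already follows all patients for survival for at least a year after the last randomisation, so no new survival data are needed. The drawback is that the by-arm OS interval will be wide, and the report should say so.

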## 9.3 Pharmacokinetic (PK) analysis

The PK's of Axitinib will be correlated with the CEPHI index. It is not currently known whether a specific level of PK is required for threshold effect on vasculature shut-down, or whether there is constant linear relationship to dose. This is the first study that may understand this better.

## 9.4 Safety Analysis

Frequencies of patients experiencing at least one AE will be displayed by System Organ Class and Preferred Term according to MedDRA terminology. Detailed information collected for each AE will include a description of the event, duration, severity, seriousness, study drug relatedness, action taken, and clinical outcome. Severity of the AEs will be graded according to the NCI CTCAE version 4.03. The analysis will be performed on AEs classified as treatment emergent.

Summary tables will present the number of patients observed with AEs and corresponding percentages. The denominator used to calculate incidence percentages consists of patients receiving at least 1 dose of study medication. Within each table, the AEs will be categorized by MedDRA system organ class and preferred term. Additional subcategories will be based on event intensity and relationship to study drug. Individual patient listings will be prepared for all AE data.

## **9.5 Analysis of clinical laboratory data**

Haematology and blood chemistry data will be graded according to NCI CTCAE version 4.03 severity grade. The frequencies of the worst severity grade observed will be displayed for each parameter.

Listing tables will be prepared for each laboratory measure, and will be structured to permit review of the data by patient as they progress on treatment. Summary tables will be prepared to examine the distribution of laboratory measures over time. Shift tables may be provided to examine the distribution of laboratory toxicities.

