Nail disorder	7 (5)		15 (19)				22 (10)	

**Table 1: Treatment-Emergent, All-Causality Adverse Events Summarized by descending frequency occurring in at least 10% of subjects with solid tumours receiving Axitinib monotherapy. Includes Protocols A4061011, A4061012, A4061014, A4061015, A4061022, A4061023, A4061027, A4061035 and A4061044.**

Laboratory test results, summarised by maximum grade for subjects with solid tumors who received single-agent Axitinib, are presented in the table below.

Group/Parameter b	N	n (%) a at Maximum Grade									
		Grade 1		Grade 2		Grade 3		Grade 4		Total	
Chemistry											
Total Bilirubin	347	44	(12.7)	21	(6.1)	2	(0.6)	2	(0.6)	69	(19.9)
Hypoalbuminemia	343	117	(34.1)	39	(11.4)	6	(1.7)	0	(0.0)	162	(47.2)
Aspartate Aminotransferase (SGOT)	347	113	(32.6)	20	(5.8)	11	(3.2)	0	(0.0)	144	(41.5)
Alanine Aminotransferase (SGPT)	345	88	(25.5)	32	(9.3)	7	(2.0)	0	(0.0)	127	(36.8)
Alkaline Phosphatase	339	108	(31.9)	26	(7.7)	6	(1.8)	0	(0.0)	140	(41.3)
Creatinine	347	103	(29.7)	25	(7.2)	0	(0.0)	4	(1.2)	132	(38.0)
Hyponatremia	347	21	(6.1)	1	(0.3)	0	(0.0)	0	(0.0)	22	(6.3)
Hyponatremia	347	108	(31.1)	0	(0.0)	16	(4.6)	0	(0.0)	124	(35.7)
Hyperkalemia	347	74	(21.3)	24	(6.9)	9	(2.6)	0	(0.0)	107	(30.8)
Hypokalemia	347	46	(13.3)	0	(0.0)	4	(1.2)	0	(0.0)	50	(14.4)
Bicarbonate	261	67	(25.7)	9	(3.4)	1	(0.4)	1	(0.4)	78	(29.9)
Hypercalcemia	171	23	(13.5)	1	(0.6)	1	(0.6)	1	(0.6)	26	(15.2)
Hypocalcemia	171	29	(17.0)	11	(6.4)	1	(0.6)	2	(1.2)	43	(25.1)
Hyperglycemia	344	158	(45.9)	56	(16.3)	13	(3.8)	0	(0.0)	227	(66.0)
Hypoglycemia	344	47	(13.7)	10	(2.9)	2	(0.6)	1	(0.3)	60	(17.4)
Hematology											
Hemoglobin	347	134	(38.6)	30	(8.6)	0	(0.0)	3	(0.9)	167	(48.1)
Platelets	346	68	(19.7)	4	(1.2)	1	(0.3)	2	(0.6)	75	(21.7)
White Blood Cells	347	52	(15.0)	12	(3.5)	0	(0.0)	1	(0.3)	65	(18.7)
Neutrophils (Abs)	344	32	(9.3)	10	(2.9)	3	(0.9)	12	(3.5)	57	(16.6)
Lymphocytes (Abs)	345	65	(18.8)	60	(17.4)	29	(8.4)	13	(3.8)	167	(48.4)
Urinalysis											
Urine Protein	337	63	(18.7)	72	(21.4)	11	(3.3)	0	(0.0)	146	(43.3)

**Table 2: Laboratory Test Results Reported for Subjects with Solid Tumors Receiving Single-Agent Axitinib Protocols A4061011, A4061012, A4061014, A4061015, A4061022, A4061023, A4061027, A4061035, and A4061044**

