## **8.4. Abnormal Test Findings**

The criteria for determining whether an abnormal objective test finding should be reported as an adverse event are as follows:

Test result is associated with accompanying symptoms, and/or;

- Test result requires additional diagnostic testing or medical/surgical intervention, and/or;
- Test result leads to a change in trial dosing (outside of protocol-stipulated dose adjustments) or discontinuation from the trial, significant additional concomitant drug treatment, or other therapy, and/or;
- Test result is considered to be an adverse event by the investigator or sponsor.

Merely repeating an abnormal test, in the absence of any of the above conditions, does not constitute an adverse event. Any abnormal test result that is determined to be an error does not require reporting as an adverse event.

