## Appendix 1 Required laboratory tests

Laboratory Test	Conventional Units	Conversion Factor	SI Units
Hematology			
hemoglobin (Hgb)	g/dL	x 10	µg/L
platelet count (Plt)	10  /mm 	x 10 	10  /L
white blood count (WBC)	10  /mm 	x 10 	10  /L
white blood cell differential	%	x 0.01	fraction
Chemistry			
total bilirubin	mg/dL	x 17.1	mmol/L
alanine transaminase (ALT)	U/L	N/A	U/L
aspartate transaminase (AST)	U/L	N/A	U/L
alkaline phosphatase	U/L	N/A	U/L
gamma-glutamyl-transpeptidase (GGT)	U/L	N/A	U/L
lactate dehydrogenase (LDH)	U/L	x 0.016667	µkat/L
total protein	g/dL	x 10	g/L
albumin	g/dL	x 10	g/L
sodium	mEq/L	x 1.0	mmol/L
chloride	MEq/L	x 1.0	mmol/L
potassium	mEq/L	x 1.0	mmol/L
calcium	mg/dL	x 0.25	mmol/L
phosphate	mg/dL	x 0.323	mmol/L
blood urea nitrogen (BUN)	mg/dL	x 0.357	mmol/L
creatinine	mg/dL	x 88.4	µmol/L
glucose	mg/dL	x 0.055	mmol/L
TSH	µU/mL		
free T3	pg/dL		
free T4	pg/dL		
Hepatocellular carcinoma tumor marker			
α-Fetoprotein	ng/mL	x 1.0	µg/L
HBV panel, HCV antibodies			
HBsAg, HBe and anti-HBc	N/A		
Anti-HCV antibodies	N/A		
Coagulation			
Prothrombin Time (or INR)	secs (or NA)	N/A	secs (or NA)
Urinalysis			
Urine protein, glucose, blood	N/A	N/A	N/A

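### The worst-grade laboratory tables in 9.5 leave out urine protein, so the toxicity comparison has no per-patient worst-grade count of proteinuria by arm

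*Combined protocol and SAP*

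**What the plan says.** Section 9.5 opens with "Haematology and blood chemistry data will be graded according to NCI CTCAE version 4.03 severity grade" and continues "The frequencies of the worst severity grade observed will be displayed for each parameter". Read in sequence, the worst-grade display covers the parameters that are graded, which are those of the two blood panels.

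Two further outputs in 9.5 are wider: "Listing tables will be prepared for each laboratory measure" and "Summary tables will be prepared to examine the distribution of laboratory measures over time". Shift tables are optional. Appendix 1 has a separate urinalysis group, "Urine protein, glucose, blood", so urine protein is a laboratory measure and these wider outputs include it.

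Blood pressure is not in Appendix 1. Sections 9.4 to 9.6 plan no safety summary of measured pressure. Diastolic pressure appears only in 9.2, as a predictor, and in two secondary endpoints, on survival and on pharmacokinetics.

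The Schedule of Activities has blood pressure at every visit. Urinalysis is at every visit except the optional one at 48-72 hours.

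The secondary endpoints in 2.2 include "To compare toxicity (CTC) information for the treatment and placebo arms".

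**The concern.** Hypertension and proteinuria are the two toxicities with their own dose-modification sections (5.11 and 5.12). Yet the plan does not say how many patients per arm reached each grade of proteinuria by measurement. A listing shows individual values, and a summary over time shows the distribution at each visit. Neither gives one worst grade per patient, which is what a toxicity comparison between arms needs.

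The protocol reports its own background data in the missing form. Table 2 in section 1.4, headed "Laboratory Test Results Reported for Subjects with Solid Tumors Receiving Single-Agent Axitinib", gives urine protein by maximum grade beside chemistry and haematology. As 9.5 stands, this trial commits to no row that could be set against it.

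Without that row, the graded count of proteinuria rests on AE reports. Section 8.4 makes an abnormal test an AE only under listed conditions, so some measured findings will not be counted. The safety figures taken forward to a phase III design could then look somewhat too favourable.

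**Working it through.** **Inputs**
- Table 2 (section 1.4), urine protein: N = 337; Grade 1: 63, Grade 2: 72, Grade 3: 11, Grade 4: 0.
- Table 1 (section 1.4), AEs: listing cut 10%; proteinuria not listed; solid-tumour single-agent column N = 128, total column N = 217.
- Table 1, hypertension in the solid-tumour column: 56, of which 22 at Grade 3/4.

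**Step 1. Reproduce Table 2.** 63 + 72 + 11 + 0 = 146, and 146/337 = 43.3%, as printed. Grade 2-3: (72 + 11)/337 = 83/337 = 24.6%. Grade 1: 63/337 = 18.7%.

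**Step 2. Bound the AE rate of an unlisted term.** The caption applies the cut to solid-tumour patients, where the largest count below 10% is 12/128 = 9.4%. The total column seems to be the one actually used: alopecia (3/128 = 2.3%, but 35/217 = 16.1%) and nail disorder (7/128 = 5.5%, but 22/217 = 10.1%) are listed. On that column the largest unlisted count is 21/217 = 9.7%, or 21/128 = 16.4% if all 21 were solid-tumour patients.

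**Step 3. Smallest share missed by AE reports** = 1 - (largest AE rate)/(laboratory rate).

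| Largest AE rate | Any grade (43.3%) | Grade 2-3 (24.6%) |
|---|---|---|
| 12/128 = 9.4% | 78.4% | 61.9% |
| 21/217 = 9.7% | 77.7% | 60.7% |
| 21/128 = 16.4% | 62.1% | 33.4% |

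The Grade 2-3 column treats every reported AE as Grade 2 or above. More than half is missed in every row for any grade, but not for Grade 2-3.

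**Step 4. Hypertension.** 56/128 = 43.8% were reported as AEs, and 22/128 = 17.2% at Grade 3/4. Nothing here suggests that raised pressure goes unreported.

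**Step 5. The AE route in this trial.** Under 8.4, a result that calls for further diagnostic testing is enough to make an AE. Section 7.4 calls for a 24-hour collection at 2+ protein, and section 5.12 at > 2+. Proteinuria that triggers the collection should therefore be reported. A lower reading with no symptoms and no consequence need not be, and a reading of exactly 2+ depends on which section is followed. The two triggers contradict each other and must be reconciled.

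Another condition in 8.4 begins "Test result leads to a change in trial dosing (outside of protocol-stipulated dose adjustments", so dose changes that the protocol prescribes do not count under it. For proteinuria this removes little: 5.12 holds dosing only after a 24-hour result, by which point the further-testing condition is already met. For blood pressure it affects mainly patients already on maximal antihypertensive treatment, whose dose is reduced with no added drug.

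**The case against.** The strongest reply is that little is lost. Urine protein is listed and summarised over time, proteinuria that changes management is reportable under 8.4, and raised pressure normally leads to drug treatment, which also meets 8.4. The same rules apply to both blinded arms, so no bias between arms is shown. In a 50-patient pilot, one more display is a matter of choice. Most of this stands, and it is why the point is minor. It does not supply a worst-grade count per patient, which neither the listings nor the summaries over time provide.

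A reader might infer three stronger things that the documents do not support.

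- *That urine protein is counted only through AE reports.* The listings and over-time summaries in 9.5 cover it.
- *That this trial would undercount proteinuria several-fold.* One could take about 33 axitinib patients (two thirds of 50) and set 33 x 0.433 = 14.3 by measurement against 33 x 0.097 = 3.2 or 33 x 0.164 = 5.4 by AE report. This sets tables with different denominators against each other (128 or 217 versus 337, where the text speaks of 364). Table 1 is limited to treatment-emergent events, while Table 2 does not say that baseline abnormalities were removed. Absence from a list gives only a bound. The AE rules of the earlier studies are not given, and this trial has its own rule and 24-hour trigger.
- *That blood pressure toxicity is under-reported.* Table 1 points the other way.

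**Conclusion.** The concern holds in a limited form. Section 9.5 restricts CTCAE grading and the worst-grade display to haematology and blood chemistry, so the CTC toxicity comparison lacks a per-patient worst-grade count of urine protein. The loss should fall mainly on dipstick readings below the 24-hour trigger.

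The size can be stated only for the earlier studies: 43.3% abnormal by measurement, against an AE rate of at most 9.4% to 16.4%. At least 62% to 78% of any-grade findings were thus absent from AE reports, and at least 33% to 62% of Grade 2-3 findings. This assumes that the two tables describe comparable patients, which their captions suggest (they name the same protocols) and their denominators put in doubt. Carrying the rates over to this colorectal population would be a further assumption that the documents do not test.

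The blood pressure part is smaller: a safety summary of measured values is absent, with no sign of lost events. Neither part touches the primary analysis.

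**What to change.** Add urinalysis to the grading sentence in 9.5. Urine protein would be graded by CTCAE version 4.03 from the scheduled dipsticks and any 24-hour result, and the number and percentage of patients at each worst grade after first dose would be shown by arm.

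Optionally, add a by-arm summary of each patient's highest clinic systolic and diastolic pressure.

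Reconcile the 24-hour collection triggers in 5.12 and 7.4, so that it is clear which dipstick readings become AEs under 8.4.

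The data are already scheduled for collection, so the cost is one or two table rows and a small text change. The only downside is that the reported toxicity figures may look slightly less favourable.
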